#### *10.2.1 Subject Disposition*

Efficacy will be evaluated on the basis of the intent-to-treat (ITT) population. A supportive analysis will also be conducted on the per-protocol (PP) population.

The intent-to-treat (ITT) population will include all subjects who received at least one dose of the study product.

The per-protocol (PP) population will include all subjects who received at least one dose of the study product with no significant protocol deviations.

The safety population (SAF) will be defined as all subjects who received at least one dose of the study product.

#### *10.2.2 Efficacy Analysis*

The primary and secondary efficacy analyses will be summarized and presented descriptively. No statistical comparison per se will be performed. However, comparison between the different doses tested may be performed.

### *10.2.3 Safety Analysis*

Safety analysis will be summarized and presented descriptively by evaluating the incidence of TEAEs and drug-related TEAEs.

### *10.2.4 Interim Analysis*

No formal interim analysis of the study endpoints is planned for this study. However, reviews of available safety data and preliminary efficacy data to guide decisions regarding the subsequent cohorts (dose decision) will be conducted by the sponsor and/or investigator(s) on an ongoing basis. Because this is an open-label study, the unblinding is not to be taken into consideration for the safety meetings.

Beyond the mainly descriptive analysis by using regular measures of central tendency and measures of dispersion, the continuous endpoints as Changes and Percentages of Changes can be assessed and tested with a mixed- effect model (Fixed-factors: treatment and time, random intercept for each patient). The least square mean and standard error of the mean will be exposed on proper plots and tables. Proportion of subjects at each time point for efficacy and safety endpoints can be compared by using contingency tables and Fisher exact test.

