## SUMMARY

**Title:** A Phase 1b, open-label, singlecenter, single-arm, dose-selection, proof-of-concept study to assess the safety and efficacy of a novel HSP90 inhibitor (CUDC-305) in the treatment of moderate to severe plaque psoriasis

**Phase:** 1b

**Population:** Approximately 12 and not exceeding 16 male or female subjects aged 18 years or older with moderate to severe plaque psoriasis will be included in this study.

**Number of Sites:** One center in Denmark will participate in this study.

**Study Duration:** Subject participation will be approximately 20 weeks, involving a 4-week screening phase, a 12-week treatment phase, and a 4-week observational follow-up phase to assess for psoriasis relapse and flare.

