## 3 STUDY ENDPOINTS

### 3.1 Primary Endpoint

The primary efficacy endpoint is as follows:

- Change from baseline in Psoriasis Area and Severity Index (PASI) score at Week 12

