#### Efficacy Endpoints

- Proportion of subjects with Physician's Global Assessment (PGA) of clear or almost clear at Weeks 2, 4, 8, 12, and 16
- Change and percent change from baseline in body surface area (BSA) covered with plaque psoriasis at Weeks 2, 4, 8, 12, and 16
- Change and percent change from baseline in BSA multiplied by the PGA at Weeks 2, 4, 8, 12, and 16
- Proportion of subjects achieving 50%, 75%, and 90% reduction from baseline in PASI at Weeks 2, 4, 8, 12, and 16
- Change and percent change from baseline in PASI scores at Weeks 2, 4, 8, and 16
- Percent change from baseline in PASI scores at Week 12
- Change from baseline in pruritus Numeric Rating Scale (NRS) at Weeks 2, 4, 8, 12, and 16
- Change from baseline in the Dermatology Life Quality Index (DLQI) total score at Weeks 4, 8, 12, and 16
- Change from baseline in skin and blood biomarkers at Weeks 4, 8, and 12

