### 10.2 Statistical and Analytical Plans

Because of the nature and design of the study, the statistical analysis will be mainly descriptive.

Descriptive summaries of demographics, baseline characteristics, and subject disposition will be presented by dose regimen and overall. Continuous variables will be summarized by dose regimen and overall in tables and will include the number of subjects, mean, standard deviation, median, minimum, maximum, and range. Categorical variables will be presented by dose regimen and overall in tables as frequencies and percentages.

Even if not sample size calculation was performed we bring a power analysis for the primary endpoint: PASI at week 12. A non parametric Wilcoxon signed-rank test will allow us to determine that Change in PASI is significant different form 0 with 80% power and 95% confidence level if the observed effect size is greater or equal to 1.23 standard deviation.

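### As written, the optional mixed model gives a dose effect averaged over visits, not the dose difference at Week 12

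*Protocol*

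**What the plan says.** The model appears in the second paragraph of Protocol section 10.2.4, as an addition to the descriptive analysis: "the continuous endpoints as Changes and Percentages of Changes can be assessed and tested with a mixed- effect model". Its terms are given in brackets as "Fixed-factors: treatment and time, random intercept for each patient". The output follows: "The least square mean and standard error of the mean will be exposed on proper plots and tables". The text does not say which visits enter, at which visit the least squares means are taken, or whether treatment and time interact.

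The primary endpoint in section 3.1 is a single time point: "Change from baseline in Psoriasis Area and Severity Index (PASI) score at Week 12". The secondary endpoints in section 3.2 add "Change and percent change from baseline in PASI scores at Weeks 2, 4, 8, and 16". The Summary describes "a 12-week treatment phase, and a 4-week observational follow-up phase to assess for psoriasis relapse and flare", so Week 16 is off treatment.

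On comparing doses, section 10.2.2 says: "No statistical comparison per se will be performed. However, comparison between the different doses tested may be performed". Section 10.2 names one test for PASI change: "A non parametric Wilcoxon signed-rank test will allow us to determine that Change in PASI is significant different form 0". Fisher's exact test, also in section 10.2.4, is for proportions.

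**The concern.** With only treatment and time as fixed factors, the fitted dose profiles are parallel. The difference between two doses is then one number, the same at every visit. It equals the Week 12 difference only if the average difference over the modelled visits happens to equal it. Change from baseline starts at zero for every subject, so differences between doses would be expected to build up over treatment, and they may shrink again at Week 16.

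The primary objective in section 2.1 is to find the effective dose range, so differences between doses are the scientific question. The mixed model is the only between-dose method that the protocol names for continuous endpoints. If dose gaps build up to Week 12, the model understates the Week 12 gap and its least squares means depart from the trial's own descriptive Week 12 means.

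**Working it through.** The protocol gives no figure for this model, so there is none to reproduce. The check is how the additive dose effect relates to the Week 12 difference.

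**Inputs from the protocol.** Model terms as quoted; change endpoints at Weeks 2, 4, 8, 12 and 16 (sections 3.1 and 3.2); four cohorts of about 4 subjects (section 4).

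**Assumptions, not in the protocol.** Onset shape f(week), scaled so that f(12) = 1: linear, f = week/12; exponential, f = (1 − e^(−week/τ))/(1 − e^(−12/τ)) with τ = 4 or 2 weeks. The share r of the effect retained at Week 16 is 1, 0.5 or 0. For precision: between-subject SD 2 and residual SD 1.5 PASI points.

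**Step 1: what the additive model estimates.** With complete data its dose contrast is the equal-weight mean of the visit-wise differences, so the ratio to the Week 12 gap is the mean of f over the visits. The contrast is the same whether time is categorical or linear.

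- Linear, Weeks 2, 4, 8, 12: (2 + 4 + 8 + 12)/(4 × 12) = 26/48 = 0.542.
- Linear, Week 16 added: (26/12 + r)/5 = 0.633, 0.533, 0.433 for r = 1, 0.5, 0.

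| Shape | Weeks 2–12 | plus Week 16, r = 1 | r = 0.5 | r = 0 |
|---|---|---|---|---|
| Linear | 0.54 | 0.63 | 0.53 | 0.43 |
| Exponential, τ = 4 | 0.75 | 0.80 | 0.70 | 0.60 |
| Exponential, τ = 2 | 0.87 | 0.90 | 0.80 | 0.70 |

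A gap constant at all visits gives 1.00. Table 1 in section 7 also schedules PASI at Weeks 1, 6 and 10. With all seven on-treatment visits, linear onset gives 43/84 = 0.51.

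**Step 2: in PASI points.** Suppose the true Week 12 changes in four cohorts are −4, −6, −8 and −10, a 6-point spread. Under linear onset the model shows 6 × 0.542 = 3.25 without Week 16, and 3.8, 3.2 or 2.6 with it (r = 1, 0.5, 0). The Week 12 least squares means without Week 16 become −5.4, −6.5, −7.5 and −8.6. With fast onset (τ = 2) and no Week 16 the spread is 5.2.

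**Step 3: check by fitting.** Two doses, 4 subjects each, true Week 12 gap −4, linear onset, half retained at Week 16, five visits, 150 simulated data sets. The additive model averaged −2.39 (Monte Carlo SE 0.12; target −2.13). The model with interaction averaged −4.26 at Week 12 (SE 0.13; target −4.00). The distance between them, 4.26 − 2.39 = 1.87, matches the expected 4.00 − 2.13 = 1.87.

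**Step 4: the price of the interaction.** With 4 subjects per dose and five visits, the SE of a dose contrast is:

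- additive: √(0.5 × (4 + 2.25/5)) = 1.49;
- dose-by-visit, at Week 12: √(0.5 × (4 + 2.25)) = 1.77.

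Fixed parameters number 1 + 3 + 4 = 8 and 4 × 5 = 20. The additive model has the smaller mean squared error for Week 12 while its bias is below √(1.77² − 1.49²) = 0.95 points (0.92 with four visits). At half retention that means a true gap below about 0.95/(1 − 0.533) = 2.0 points (linear) or 4.7 (τ = 2). Without Week 16 the limits are about 2.0 and 7.1.

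**Step 5: interval coverage.** In simulation (20,000 runs per setting, nominal 95%, Week 16 included), the additive interval covers a true Week 12 gap of 6 in 36% of runs (linear, r = 0), 51% (linear, r = 0.5), 74% (τ = 4, r = 0.5) and 84% (τ = 2, r = 0.5). For a gap of 2 it covers in 85–92%. The dose-by-visit interval covers in 93–94% throughout.

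**The case against.** The strongest objection is that this is detail for the statistical analysis plan, which is not shown. The bracket lists factors; it is not a full model equation and does not exclude an interaction. That is fair, and the point is limited to the model as written. But the protocol did not leave the model open: it names the fixed factors and the random term, and a reader who fits them gets the averaged effect.

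Second, no section says that this model will estimate the Week 12 dose difference. The efficacy analyses are descriptive, the model is optional, and an across-visit effect is a legitimate summary of repeated changes. This limits the consequence. Still, the least squares means are to be tabulated without a stated visit, and no other between-dose method is named for the primary endpoint.

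Third, with about 4 subjects per dose a sparse model can be the better choice. This stands in part: for small gaps, or moderate gaps with fast onset, the additive model has the lower mean squared error. That trade-off can be chosen, but the protocol does not say that it has been.

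Finally, the sizes rest on assumed onset shapes and SDs, and the lowest coverage figures need linear onset, a large gap and Week 16 in the model. Cohorts are also filled sequentially, not by randomisation (section 6.2.6), so any dose contrast is exploratory. Both are true. Neither changes what the additive model estimates.

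**Conclusion.** The point holds as a minor one. Read literally, section 10.2.4 describes a model whose dose effect is the visit average and not the difference in the primary endpoint. The distortion runs from none (constant gap) to a little over half of the Week 12 gap lost (ratio 0.43: linear onset, Week 16 included, nothing retained). Without Week 16 the loss under the assumed shapes is 13% to 46%. These sizes assume complete data and the stated shapes; the protocol supplies none. The descriptive Week 12 summaries, the Wilcoxon test against zero and the dose-decision meetings are unaffected. If an interaction is intended, the text only needs to say so.

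**What to change.** In section 10.2.4, if the model is kept, state: fixed factors dose, visit (categorical) and dose-by-visit, with a random intercept for each patient; least squares means and dose contrasts with 95% confidence intervals reported at Week 12; Week 16 shown as a separate off-treatment visit. A lighter alternative for the dose comparison is an ANCOVA of Week 12 PASI change on dose and baseline PASI, with 1 + 3 + 1 = 5 parameters.

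The change is wording only and needs no new data. It costs precision: under the SDs assumed above, the SE of a dose contrast is 1.77 instead of 1.49 points. For the ANCOVA it is about 1.86 if baseline is unrelated to change (8,000 simulated runs, baseline PASI uniform on 6 to 24). If the sponsor prefers the additive model for its smaller variance, the protocol should say that its dose effect is an average over named on-treatment visits and should not label it a Week 12 difference.

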## 4 STUDY DESIGN

This is a 12-week treatment, singlecenter, open-label, single-arm, dose-selection, proof-of-concept study to determine a dosage of CUDC-305 that is tolerable and demonstrates preliminary efficacy for use in future efficacy Phase 2 trials.

Eligible subjects will be sequentially assigned to one of the four cohorts (approximately n = 4 per cohort) receiving ascending or descending doses of CUDC-305. The first cohort will be administered a starting oral dose of 250 mg/d for 12 weeks, which is believed to be the target effective dose for treatment of psoriasis. The dose regimen to be administered to the subsequent cohort will be decided after reviewing the safety and efficacy data of the first four subjects completing the treatment period (12 weeks) in the current cohort. A safety meeting will take place to review the available data prior to deciding the next dose and then initiating dosing of the subsequent cohort. The doses that will be evaluated in this study range between 100 mg and 1000 mg and may include: 100 mg, 250 mg, 500 mg, 800 mg, or 1000 mg orally once daily.

The sponsor and principal investigator(s) will jointly evaluate the safety and tolerability of CUDC-305 at the safety meeting, and intolerance will be determined by taking into account all information from adverse events (AEs), vital signs, physical examination findings, laboratory abnormalities, and electrocardiogram (ECG) findings. The study may be stopped permanently or interrupted at any time for safety reasons.

PASI, PGA, BSA, pruritus NRS, and DLQI will be performed to assess efficacy. Safety will be assessed with the vital signs, physical examination, clinical laboratory tests, ECG, and collection of AEs.

Skin biopsies will be collected from nonlesional and lesional skin for immunohistochemistry and gene expression analysis.

Medical photographs of the target lesion will also be performed at each study visit (except the screening visit).

A schedule of events is presented in Section 7.

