## 10 SAMPLE SIZE AND STATISTICAL METHODS

### 10.1 Determination of Sample Size

No formal sample size calculations were conducted. Six subjects will be enrolled into each cohort, for a total of maximum 16 subjects. This sample size was selected to allow sufficient characterization of the drug's safety profile over the planned doses range and to allow for preliminary efficacy assessments of CUDC-305 in subjects with moderate to severe plaque psoriasis.

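### Section 10.2.4 shows dose-level efficacy as least square means with standard errors and names no confidence interval; at about four subjects per dose, a 95% interval would be the better display

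*Protocol*

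**What the plan says.** The second paragraph of protocol Section 10.2.4 goes beyond the descriptive summaries. It says that "the continuous endpoints as Changes and Percentages of Changes can be assessed and tested with a mixed- effect model", with treatment and time as fixed factors and a random intercept per patient. The display follows: "The least square mean and standard error of the mean will be exposed on proper plots and tables". The model is optional, but the display is worded as definite.

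Section 10.2 also requires by-dose and overall tables. For continuous variables these "will include the number of subjects, mean, standard deviation, median, minimum, maximum, and range". For the rest, "Categorical variables will be presented by dose regimen and overall in tables as frequencies and percentages". Section 10.2.4 adds that proportions "can be compared by using contingency tables and Fisher exact test".

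No section names a confidence interval for a dose-level mean or proportion. The only mention of confidence is the level quoted in the power sentence of Section 10.2.

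On numbers, Section 4, Section 6.2.6 and the Summary put about four subjects in each of four cohorts, and the Summary gives about 12 and at most 16 subjects in all. Section 10.1 differs: "Six subjects will be enrolled into each cohort, for a total of maximum 16 subjects".

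**The concern.** The primary objective is an efficacious dose range, and the trial is meant to recommend a dose for Phase 2. The analysis is mainly descriptive. Section 10.2.2 plans no formal comparison but allows doses to be compared. Much of the reading of dose against response will therefore be done by eye, from plots and tables by dose.

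A standard error shown beside each estimate suits that use poorly. A ±1 SE bar looks like a range of plausible values but is much narrower than a 95% interval, and the gap is widest when few degrees of freedom are available. With several small cohorts side by side, some bars will often separate by chance, and a reader may take that as a dose difference. What is at stake is how the dose finding is read, not the validity of a test.

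**Working it through.** **The protocol's own figure.** The protocol attaches no number to this display, so there is nothing to reproduce. Its one design figure (80% power at 1.23 SD, Section 10.2) concerns a test of PASI change against zero and does not bear on this point.

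**Inputs.**
- n = 4 per dose (Section 4); n = 6 as a sensitivity case (Section 10.1).
- k = 3 or 4 doses, since 12/4 = 3 and 16/4 = 4; k = 2 for a single pair.
- Assumed, because the protocol does not say: a plotted SE is drawn as ±1 SE, and outcomes are normal with equal variance. The SD of PASI change is not given, but it cancels from every result on bars.

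**Step 1: coverage of ±1 SE.** Coverage = P(|T| < 1) for a t-variable.
- Own SE, n − 1 = 3 df: (2/π)(π/6 + 0.5 × 0.866) = 0.609.
- Pooled SE over four doses, 4 × 3 = 12 df: 0.663.
- Multiplier needed for 95%: 3.18 (3 df) or 2.18 (12 df).

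**Step 2: how often identical doses appear separated.** Two bars fail to overlap when |m_i − m_j| > SE_i + SE_j. With a common pooled SE, at least one pair separates when the range of the means exceeds 2 SE. That probability is P(q > 2; k, k(n − 1)) for the studentized range q. The own-SE case was simulated (300,000 trials per setting). The pooled case was both simulated and computed from the studentized range: 0.207 and 0.207 for k = 2, 0.376 and 0.374 for k = 3, 0.514 and 0.515 for k = 4.

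Chance of at least one non-overlapping pair at one time point, all doses identical, n = 4:

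| Doses | ±1 SE, own | ±1 SE, pooled | 95% t-interval, own | 95% t-interval, pooled |
|---|---|---|---|---|
| 2 | 22% | 21% | 0.5% | 1.3% |
| 3 | 45% | 38% | 1.5% | 2.7% |
| 4 | 62% | 51% | 2.7% | 4.1% |

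In balanced data the additive random-intercept model gives every dose the same SE, so the pooled columns are the closer match to Section 10.2.4. If LS means are plotted for each visit, their SE also carries the error of the time effect, and separation would be somewhat rarer.

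**Step 3: sensitivity.** With n = 6 and four doses, the ±1 SE figures are 57% (own) and 51% (pooled). In very large samples they tend to 16%, 33% and 49% for two, three and four doses. Most of the effect therefore comes from 1-SE bars across several doses; the small cohorts add the rest.

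**Step 4: proportions (supporting).** Exact 95% limits at n = 4:
- 0/4: upper limit 1 − 0.025^(1/4) = 0.60, so 0–60%.
- 2/4: 7–93%.
- 4/4: lower limit 0.025^(1/4) = 0.40, so 40–100%.

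Fisher's exact test at 4 v 4 gives p = 0.14 for 3/4 v 0/4; only 4/4 v 0/4 falls below 0.05 (p = 0.029).

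**The case against.** The best case for leaving the text alone has four parts.

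- **The display is secondary.** The mixed model is optional. The core output is the by-dose tables, and at n = 4 the minimum, median and maximum come close to listing the data. This stands and lowers the weight of the point. It does not change what the LS mean plots would show.
- **A reader can rebuild the interval.** Given mean, SE and n, the t-interval follows. That is true of a table, but a plot is read by eye.
- **Interval method and plot format often sit in an SAP.** This stands for the proportions, where nothing in the protocol rules intervals out, so those are only an addition. For continuous endpoints the protocol itself names the standard error.
- **No rule selects a dose by bar overlap.** This also stands. Sections 4 and 6.2.6 base the next dose on review of safety and efficacy data. The figures above describe how a display may be misread, not the error rate of a planned decision.

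A reader might go further in three ways that the text does not support.

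- One might take the bars to be raw SEMs that do not belong to the LS means. In a sentence that follows a mixed model, the natural reading is the SE of the LS mean, so 51% is the better four-dose figure than 62%.
- One might call the percentages bare. Frequencies accompany them, a Fisher test is allowed, and no plot of proportions is described.
- One might say that Section 10.1 calls four per dose enough for safety. Its sentence gives six per cohort, and its claim, "to allow sufficient characterization of the drug's safety profile over the planned doses range", refers to the range of doses and not to each one.

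**Conclusion.** The point holds as a recommended improvement. The protocol chooses a standard error as the displayed uncertainty for dose-level efficacy and names no interval. At about four subjects per dose that display has 61–66% coverage. Identical doses would show at least one separated pair at a time point in roughly one trial in five with two doses, 38–45% with three and 51–62% with four, against about 3–4% for four doses with 95% t-intervals. The lower, pooled figures are the more likely to apply.

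The results rest on normal outcomes, equal variances, bars drawn at ±1 SE and balanced cohorts; they do not depend on the SD. It would be too strong to say that the display makes identical doses look different as a matter of course, or that it is an error: separation is a probability, and for a single pair overlap is much the likelier outcome.

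**What to change.** In Section 10.2.4, replace the standard error with the model-based 95% confidence interval of the LS mean on small-sample degrees of freedom, in both tables and plots. Ideally plot the individual values as well, which is easy with about four points per dose.

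As a supporting addition, here or in the SAP, report responder and TEAE proportions by dose as x/n with exact 95% intervals.

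Before any precision statement is added to Section 10.1, reconcile its six per cohort with the four given elsewhere. Six in each of four cohorts would be 6 × 4 = 24 subjects, above the stated maximum of 16.

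The cost is a few lines of wording and no new data. The drawback is that the intervals will be wide (2.18 to 3.18 times the SE on each side) and will look less favourable.
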